 Where clinical chemistry test is conducted, serum phosphorus, serum total corrected calcium and albumin will be included therefore separate tests are not required at these visits.

 Wherever possible a sample for central laboratory analysis of these parameters should be obtained at the final visit of Stage 1.

 Exclude these blood tests in subjects <36 months but provide value if available from routine clinical assessment. Samples for bone marker assessment will be obtained and may be stored (frozen) for later

 Any visit where this value is available from routine clinical assessment.

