# 2.5. Efficacy, Pharmacokinetic, and Safety Variables

## 2.5.1. Efficacy Variables

## 2.5.1.1. Primary Efficacy Endpoint

The primary efficacy endpoint is the change in serum phosphorus levels from baseline to the end of Stage 1 in PA21 group. It is based on central laboratory data; in case of missing data, the change from baseline will be computed using pre- and post-treatment values from the local laboratory (see Section 4.2.8).

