## 2.5.3.2. Secondary Safety Endpoints

The following safety secondary endpoints are planned for analysis:

- Serum total corrected calcium at each time point and change from baseline
- Percentage of subjects who develop at least 1 episode of sustained hypercalcaemia (defined as total calcium value>upper safety limit from Table 6 (Table J from the study protocol synopsis) confirmed by repeat sample 1 week later) after start of treatment
- Serum total corrected calcium-phosphorus product at each time point and change from baseline, where serum total corrected calcium-phosphorus product correspond to the product of serum total calcium and Phosphorus, expressed in mmol/L (serum total calcium and Phosphorus units must be the same).
- Serum iPTH levels at each time point and change from baseline
- Routine biochemical/haematological laboratory tests (blood iron parameters, Vitamin D parameters and bone markers)
- Vital signs

Table 6 Age Related Safety Limits of Total Calcium

Age	Upper S	afety Limit	Lower Sa	fety Limit
	mmol/L	mg/dL	mmol/L	mg/dL
0 to <1 year	2.75	11.0	<1.9	<7.6
≥1 year to <6 years	2.70	10.8	<1.9	<7.6
≥6 years to <13 years	2.60	10.3	<1.9	<7.6
≥13 years to ≤18 years	2.60	10.2	<1.9	< 7.6

Note: Upper safety limits were based on National Kidney Foundation Kidney Disease Outcomes Quality Initiative Nutrition Guidelines, 2008. Lower limit were based on literature (Paediatric Nephrology, 2nd edition) and personal communication. Both limits were slightly modified to include 18 year in the last category.

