#### 4.2.9. Visit Windows

The below windowing will be applied for summary tables with descriptive statistics over time, label of the visit will be derived as below.

Analysis visit	Week number	Windowing
Visit 5	Day 1 (Baseline) Stage 1	Day 1 (Visit 5)
Visit 6	Week 1 - Stage 1	Day 8 (+/- 3 days)
Visit 7	Week 2 - Stage 1	Day 15 (+/- 3 days)
Visit 8	Week 4 - Stage 1	Day 29 (+/- 3 days)
Visit 9	Week 6 - Stage 1	Day 43 (+/- 3 days)

Visit 10	Week 8 - Stage 1	Day 57 (+/- 3 days)
Visit 11	Week 10 - Stage 1	Day 71 (+/- 7 days)
N/A	Day 1 (Baseline) Stage 2	Day 1 (last visit in the titration phase + 1)
Visit 12	Week 4 - Stage 2	Day 29 (+/- 3 days)
Visit 13	Week 8 - Stage 2	Day 57 (+/- 3 days)
Visit 14	Week 12 - Stage 2	Day 85 (+/- 3 days)
Visit 15	Week 18 - Stage 2	Day 127 (+/- 7 days)
Visit 16	Week 24 - Stage 2	Day 169 (+/- 7 days)

If several values are falling into the same time window then the nearest value compared to the pre-defined week window as per protocol will be considered for efficacy and safety, if they are still 2 or more values then the first one in time among the nearest value will be considered. In case of 2 values at the same time (planned visit and unscheduled one), then the planned visit will be considered.

In addition, visit 11 or earlier (visit when "Yes" is responded to the question "Will subject enter the Stage 2 Safety Extension period after the current visit?") and visit 16 or earlier data will be reported with the corresponding label in the summary tables "End of Stage 1" and "End of Stage 2", respectively. If subject withdrew during stage 1, visit 16 will be displayed with the corresponding label in the summary tables "End of Stage 1".

For "End of Stage 1" and "End of Stage 2" reported visits of the safety analyses, the original visits (as collected in the EDC system and not derived) will be used. The last non missing assessment collected in each period will be reported under "End of Stage 1" and "End of Stage 2".

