## 4.7. Efficacy Evaluation

Efficacy analysis will be conducted using the FAS and PPS Populations as outlined below.

All results related to serum phosphorus will be expressed in both mmol/L and mg/dL units.

Standard units (mmol/L) from the laboratory file sent by the external vendor will be used to derive the unit in mg/dL using the following conversion factor: ×3.096, starting from the standardized result.

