#### 4.9.2. Secondary Safety Endpoints

For serum total corrected calcium and serum total corrected calcium-phosphorus product expressed in mmol/L and mmol/L respectively, absolute value and change from baseline value

based on both central and local laboratory data, separately, will be described at each time point by treatment group.

For serum intact parathyroid hormone (iPTH) levels, absolute value and change from baseline value based on central laboratory data will be described at each time point by treatment group and will be expressed in both pmol/L and ng/mL units.

Percentage of subjects who develop at least 1 episode of sustained hypercalcaemia (defined as total calcium value>upper safety limit from Table 6 confirmed by repeat sample 1 week later) after start of treatment will be provided by treatment group. All the records from the local and central laboratories including scheduled and unscheduled visits will be taken into account. Patient will be considered as having an episode of sustained hypercalcaemia if two consecutive assessments separated by 6 days or more have calcium value greater than the upper limit of safety.

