#### 4.9.3. Laboratory Data

Clinical laboratory values will be expressed using SI units.

The actual value and change from baseline will be summarised for each clinical laboratory parameter at each time point by treatment group based on central laboratory measurements. For serum phosphorus, calcium (total and corrected) and albumin chemistry parameters, both central and local laboratory summary tables will be provided.

Shift tables from baseline to each post-baseline visit will be produced using the low/normal/high classification based on laboratory reference ranges.

The normal ranges of some parameters from the central laboratory data are only available for the age group above or equal to 18 years and not from 0 to 17yrs; therefore shift tables will not produce for the below parameters due to missing normal ranges. Only Actual Values and Changes Over Time tables and listings will be presented.

- Ferritin
- Osteocalcin
- Transferrin
- Vitamin A
- Vitamin E
- Vitamin K
- Intact parathyroid hormone
- Fibroblast growth factor 23
- Tartrate-resistant acid phosphatase 5b
- Atypical lymphocytes and Lymphocytes atypical/leukocytes

All laboratory data will be provided in data listings.

A subset listing will be presented for all abnormal laboratory values.

**Table 10** List of Laboratory Parameters

Category	Parameters
Haematology	Erythrocytes, Mean corpuscular volume, Mean corpuscular haemoglobin
	Mean corpuscular haemoglobin concentration, Haemoglobin, Haematocrit
	Reticulocyte count, White blood cells, White blood cell differential (% and absolute value), Neutrophils, Eosinophils, Basophils, Lymphocytes, Monocytes, Platelets
Chemistry	Calcium (total, corrected), Intact parathyroid hormone (only shift tables as already summarised as part of the secondary safety endpoints), Creatinine, Glucose, Triglycerides, Total protein, Albumin, Urea, Uric acid, Total bilirubin, Total cholesterol (differential in high density lipoproteins and low density lipoproteins), Creatine phosphokinase, C-reactive protein, Bicarbonate, Sodium, Potassium, Chloride
Chemistry – Liver Enzymes	Alkaline phosphatase, Aspartate transaminase, Alanine transaminase, Lactate dehydrogenase, Gamma-glutamyl transpeptidase
Iron Status Parameters	Iron, Ferritin, Transferrin, Unsaturated Iron Binding Capacity, Transferrin saturation
Vitamins	A, 25(OH)D, 1,25(OH)2D, E, K
Bone Markers	Carboxyterminal cross-linking telopeptide of bone collagen,

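### The derivation of sustained hypercalcaemia in SAP 4.9.2 can cancel an episode confirmed at one week when an extra high sample falls in between; the unit columns of Table 6 also need reconciling

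*SAP*

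**What the plan says.** Section 2.5.3.2 lists, as a secondary safety endpoint, the percentage of subjects with at least one episode of sustained hypercalcaemia after treatment starts, "defined as total calcium value>upper safety limit from Table 6 (Table J from the study protocol synopsis) confirmed by repeat sample 1 week later".

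Section 4.9.2 repeats that definition and adds how the data are to be processed. On the input it says "All the records from the local and central laboratories including scheduled and unscheduled visits will be taken into account". On the decision, a patient has an episode if "two consecutive assessments separated by 6 days or more have calcium value greater than the upper limit of safety". The document history records that details on deriving an episode were added to this section, so this sentence is the rule to be programmed for Table 14.4.6.

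Table 6 gives the upper limits by age in two units:

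| Age | mmol/L | mg/dL |
|---|---|---|
| 0 to <1 year | 2.75 | 11.0 |
| 1 to <6 years | 2.70 | 10.8 |
| 6 to <13 years | 2.60 | 10.3 |
| 13 to 18 years | 2.60 | 10.2 |

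The lower limit is 1.9 mmol/L, or 7.6 mg/dL, at all ages. On units, Section 4.9.3 says "Clinical laboratory values will be expressed using SI units". Section 4.2.1 makes SI the default for both laboratory sources, and Section 4.9.2 expresses corrected calcium in mmol/L. For phosphorus, Section 4.7 derives mg/dL "using the following conversion factor: ×3.096". No factor is given for calcium.

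**The concern.** The definition asks whether a high value is still high about a week later. The derivation asks something slightly different: whether two *adjacent* records are both high and at least 6 days apart. The two agree when there is nothing between the first sample and its one-week repeat. They part when a further high sample is drawn in between, because the one-week pair is then no longer adjacent and each shorter gap may fall below 6 days. More evidence of sustained elevation then produces a negative result.

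Table 6 raises a separate matter. One mmol/L limit stands beside two different mg/dL limits, so the two columns cannot be the same set of cut-offs, and the endpoint rule cites the table without naming a column.

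At stake is a named safety endpoint in a trial whose comparator is a calcium-based binder. At the planned size of about 30 subjects on Phoslyra, one reclassified subject moves the percentage by 1/30 = 3.3 points; among about 100 on PA21, by 1 point.

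**Working it through.** **Pairing rule.** The literal rule is that some adjacent pair of records is high on both sides with a gap of at least 6 days. The comparison rule is an unbroken run of high records whose first and last are at least 6 days apart.

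| Sequence (study day) | Gaps between adjacent highs | Literal | Run-based |
|---|---|---|---|
| High 29, high 36, normal 43 | 7 | episode | episode |
| High 29, high 32, high 36, normal 43 | 3, 4 | none | episode |
| High 0, 3, 7, 11, 14 | 3, 4, 4, 3 | none | episode |
| High 0, normal 3, high 7 | no adjacent highs | none | none |

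The second row contains the first: Day 36 is a high repeat 7 days after Day 29, as the definition requires.

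In general, take a high on day 0, a high repeat on day 7 and a normal reading on day 14.

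- One high recheck on day k leaves gaps of k and 7 − k. One of them reaches 6 only if k = 1 or k = 6. So the episode is lost for k = 2, 3, 4 and 5, which is 4 of the 6 possible days.
- Two high rechecks on different days leave three gaps of at least 1 day that sum to 7. The largest possible is 5, so the episode is lost in all 15 placements (6 × 5 / 2).

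These are counts of possible timings, not probabilities.

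**When it can arise.** Table 3 schedules post-baseline calcium at Weeks 2, 4, 6, 8 and 10 and then at wider intervals. Table 2 allows ±3 days around each visit. The shortest scheduled interval is therefore 14 − 3 − 3 = 8 days, so scheduled samples alone cannot produce the problem. Three samples within 7 days need at least two off schedule; an early-withdrawal visit could be one. The one-week repeat is itself off schedule. Finally, the next reading must not be high 6 or more days after the last: if Day 43 had been high in the second row, the gap 43 − 36 = 7 would have restored the episode.

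**Table 6.** Ratios of mg/dL to mmol/L:

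- 11.0/2.75 = 4.000; 10.8/2.70 = 4.000; lower limit 7.6/1.9 = 4.000
- 10.3/2.60 = 3.962; 10.2/2.60 = 3.923

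At 4.00, 10.3 mg/dL is 2.575 mmol/L (0.025 below 2.60) and 10.2 mg/dL is 2.55 mmol/L (0.05 below).

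Rounding of the printed figures allows a factor from (mg/dL − 0.05)/(mmol/L + 0.005) to (mg/dL + 0.05)/(mmol/L − 0.005):

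| Age | Factor range |
|---|---|
| 0 to <1 year | 3.975 to 4.026 |
| 1 to <6 years | 3.974 to 4.026 |
| 6 to <13 years | 3.935 to 3.988 |
| 13 to 18 years | 3.896 to 3.950 |

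The last range lies wholly below the first two, so no single factor fits all four rows. Rounding 2.575 and 2.55 to 2.6 before printing 2.60 would explain the older rows, but the table prints 2.75 at two decimals and does not say that precision varies. By contrast, all 20 phosphorus pairs (8 in Table 4, 12 in Table 5) agree to one decimal at the stated 3.096.

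**The case against.** **On the pairing rule.** The decision sentence says *if*, not *only if*, and the definition stands in the same paragraph, so a sensible programmer could still count the Day 29 and Day 36 patient. That looser reading is available but not written down. A sentence added as the derivation will be programmed as one, so the objection does not remove the need for rewording. The objection that the case is narrow stands in full: off-schedule samples are needed, and so is the absence of a later high reading at the required distance.

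**On Table 6.** A reader might infer that children aged 6 and over will be misclassified in the 0.025 and 0.05 mmol/L bands. The SAP does not support that. Dual units are specified for phosphorus and iPTH, not for calcium, and Sections 4.2.1, 4.9.2 and 4.9.3 together point to mmol/L. With values in mmol/L, 2.60 applies to both older bands and the mg/dL column reclassifies nobody. What survives is the possibility that the mmol/L column is the one that departs from the source, which the SAP cannot exclude.

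**On same-day readings.** A reader might also infer that discordant local and central values on one day make the result depend on sort order. The SAP describes no sort. Table 3 footnote 5 asks for a central sample at the end of Stage 1 where possible but does not say that a local one is drawn as well. Giving central values precedence would discard high local values that Section 4.9.2 says are to be used. I make no point of this.

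**Conclusion.** The derivation in Section 4.9.2, read literally, contradicts the definition it is meant to implement: an extra high sample can turn a confirmed episode into none. This is certain as logic and rests only on taking *consecutive* to mean adjacent among all the records the SAP admits. Its effect on the reported percentage cannot be computed, because the SAP does not show how often off-schedule rechecks occur. The literal rule can only undercount relative to the run-based one, since any adjacent high pair at least 6 days apart is itself a qualifying run.

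The Table 6 mismatch is real but secondary. It changes a classification only if mg/dL is used or if 2.60 mmol/L is not what the source gives. Which limit is right cannot be settled from the SAP.

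Both should be corrected before lock. The endpoint is descriptive, and neither point touches the primary efficacy analysis.

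**What to change.** 1. In Section 4.9.2, replace the decision sentence with: an episode is an unbroken run of readings after the first dose, all above the age-related upper limit, whose first and last readings are at least 6 days apart. This keeps the existing 6-day threshold and the full set of records, and a normal reading in between still breaks the run.
2. Before lock, reconcile the two columns of Table 6 with Table J of the protocol synopsis and the source cited under the table, and state in Section 4.9.2 which column is applied.

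The cost is one changed sentence and one added sentence in Section 4.9.2, one revised derivation for Table 14.4.6, and one check of a table against its source. No new data are needed.

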## 2.5.3.3. Other Safety Endpoints

Safety assessments performed during the study including physical examinations.

#### 2.5.4. Other Variables

# 2.5.4.1. Subject Reported Palatability and Acceptability

Age-appropriate assessments will be used based on already-established and standardised versions of the combined facial/hedonic and 10 cm visual analogue scale.

## 3. SUBJECT POPULATIONS

# 3.1. Population Definitions

The following subject populations will be evaluated and used for presentation and analysis of the data:

- Full Analysis Set (FAS) Population: all subjects randomised to treatment at Stage 1, who received at least one dose of randomised treatment and who had at least one post-baseline assessment of the efficacy endpoint (serum phosphorus level). FAS population will be analysed according to treatment randomised. This population will be analysed for the protocol deviations, demographics and baseline characteristics, medical history and efficacy endpoints.
- Per Protocol Set (PPS) Population: all subjects in the FAS population who had no statistical major protocol violations. This population will be analysed for the demographics and baseline characteristics, medical history as well as for the primary and secondary efficacy endpoints
- Safety Population: all subjects who have taken at least one dose of study medication. Safety population will be analysed according to treatment received.
- Stage 2 Safety Population: all subjects who have taken at least one dose of study medication during stage 2.

If a subject switches from a treatment to the other by mistake, then other safety populations will be created to report the adverse events under each received treatment.

The FAS Population is the primary population for the analysis of efficacy parameters. A subset of efficacy parameters will be evaluated for the PPS Population. The Safety Population is the population for the analysis of safety endpoints. If a subject switches from a treatment to the other by mistake, further adverse events summary tables will be generated using additional safety populations.

#### 3.2. Protocol Violations

The sponsor trial statistician with the Clinical Research Manager and the Clinical Trial Manager using the SAP and the final and consolidated versions of the Important and Non-important Protocol Deviations Designation and Escalation files (produced by Covance) will produce a protocol deviation criteria list to review, assess all protocol deviations (programmable deviations and deviations captured by the CRA) and classify as major deviations those which lead to exclusion of a subject's data from the PPS Population.

Covance will be responsible to review programmable PDs listing provided by Cytel on a quarterly basis and reconcile them to produce the final protocol deviation file (formatted as a Microsoft Excel file). This file will include the Important and Non-important Protocol Deviations Designation and Escalation lists as well as the programmable PDs. The protocol deviation file reconciled by Covance will include subject number, deviation code and a description of the protocol deviation.

The protocol deviation criteria list provided by the sponsor will specify the list of all protocol deviations and for each deviation a deviation code, and will identify whether or not the deviation

may warrant exclusion from the PPS Population. The final and reconciled protocol deviation file provided by Covance will be sent to the sponsor.

The sponsor will be in charge to review, update this file with the information coming from protocol deviation criteria list and send back to Cytel. This final file will be reviewed during the blinded data review meeting and finalised prior to hard database lock.

The major protocol deviations are as follows:

- Subject with insufficient compliance, i.e. missing, <70% or >120% during stage 1 or stage 2, (programmatically derived)
- Randomized subjects not fulfilling inclusion criterion number 2 on Hyperphosphatemia values (according to age) before randomisation (programmatically derived)
- Subjects with no baseline serum phosphorus value (programmatically derived)
- Subject with End of stage 1 visit date outside of allowed visit windows (section 4.2.9) (programmatically derived)
- Incorrect study treatment (not compliant with the IxRS randomisation) given to the subject (programmatically derived)
- Subjects who received both PA21 and Phoslyra (programmatically derived)
- Subject was randomised but did not meet inclusion criterion 4 or 5 (programmatically derived).
- Subject was randomised but met exclusion criterion 1, 2, 11 or 12 (programmatically derived).
- ICF not signed or signed by parents/guardian after randomisation date and if child is 7 or older, assent not obtained or obtained after randomisation date (programmatically derived).
- Other from deviations identified during the study which may lead to classification of "Major" as per clinical judgment during the blinded Data Review Meeting. If these deviations could not be programmatically derived, then an excel file will be provided by the sponsor with the corresponding major deviation information.

All protocol deviations will be presented in the data listings.

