#### 2. STUDY DESIGN

# 2.1. Synopsis of Study Design

This study is a prospective, open-label, randomised, active-controlled, parallel group, multicenter, phase 3 study investigating the safety and efficacy of PA21 (Velphoro®) and calcium acetate (Phoslyra®) in paediatric and adolescent CKD subjects with hyperphosphataemia.

Approximately 130 subjects will be randomised to either PA21 (approximately 100 subjects) or to Phoslyra (approximately 30 subjects) with age as stratification factor.

Throughout the study, subjects randomised to receive PA21 will be provided with the most appropriate formulation i.e., either powder for oral suspension (for subjects <6 years) or chewable tablet (for subjects ≥6 years). For Phoslyra, only oral solution will be dispensed.

The study will consist of a maximum of 43 weeks including a screening period, a washout period, a treatment period split into 2 stages, and a follow-up period. Screening should be up to 4 weeks. The washout period should be of 1-3 weeks to allow sufficient time for washout of previous Phosphate Binders (PBs). Of note, subjects already receiving a PB but with age related serum phosphorus levels (Table H of the protocol) may be eligible for randomisation without a washout period. Treatment period will be split in 2 stages:

- Stage 1 is a dose titration period of PA21 and Phoslyra for up to 10 weeks. PA21 subjects will receive PA21 at a starting dose based on their age, as detailed in Table 3 from protocol. Phoslyra subjects will receive Phoslyra, either at a starting dose as detailed in Table 5 from protocol, or, if considered more appropriate by the Investigator, at an equivalent dose of their previous PB, calcium-based or sevelamer. Doses of PA21 or Phoslyra will be increased or decreased as required for efficacy (to achieve age specific target serum phosphorus level as indicated in Table 11 from protocol), provided a subject has been receiving that dose for a minimum of 2 weeks, and for safety or tolerability reasons at any time. Increases or decreases in dose and maximum doses are detailed in Table 4 from protocol for PA21, and Table 5 and Table 6 from protocol for Phoslyra. From Week 4, once a subject achieves the age specific target serum phosphorus level, as indicated in Table 11 from protocol, they can move to Stage 2.

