#### 1. PA21

## 2. Phoslyra

A 'Total' column will be used in all the outputs, which will present a total over both treatment groups, with the exception of exposure data where data will be presented separately for each drug.

Tabulations will be produced for appropriate demographic, baseline, efficacy and safety parameters. For categorical variables, summary tabulations of the number and missing observations as well as the number and percentage within each category of the parameter will be presented. For continuous variables, the number and missing observations, mean, median, standard deviation, Q1, Q3, minimum, and maximum values will be presented.

For the laboratory parameters, the number of the decimal places (dp) will be determined using the following rules based on the number of dp from the raw data:

- mean, median, q1 and q3 = raw + 1
- sd = raw + 2
- Min and max = raw

Formal statistical hypothesis testing will be performed on the primary endpoint only with test conducted at the 2-sided, 0.05 level of significance. Summary statistics will be presented, as well as confidence intervals on selected parameters, as described in the sections below. Some other statistical tests within each group may be performed for the secondary efficacy endpoints depending on the observed clinical differences.

Baseline will be defined as the latest measurement collected prior to first dose of study treatment.

Stage 1 data will be defined as all data collected until the last visit in the titration phase (prior to visit 12 and when "Yes" is responded to the question "Will subject enter the Stage 2 Safety Extension period after the current visit?"). Of note, if subject withdrew during stage 1 (i.e. no stage 2 initiated), visit 16 will be considered as part of stage 1.

Stage 2 data will be defined as all data collected from the day after the last visit in the titration phase.

Both local and central laboratory data will be reported using SI units, unless otherwise specify.

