## 4.6. Exposure to Study Drug

Exposure to study drug will be summarised for each drug separately and for stage 1, stage 2 and overall study using descriptive statistics. Summary tables will be generated on the Safety Population for stage 1 and overall study exposure and on the Stage 2 Safety Population for stage 2 exposure data. They will include:

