- For Phoslyra drug:[[473\* total number of bottles dispensed (473\* total number of unused bottles + 473\* total number of bottles reported as lost + sum of mL left from the total number of partially used bottles returned)] / total prescribed dose (in mL)]\*100, where the total prescribed dose corresponds to ∑i=1n (end date start date of administration(i) +1) \* Prescribed dose of administration(i) (in mL/day) as defined earlier. The prescribed dose (in mL/day) from the Phoslyra dosing eCRF page will be considered. Of note for the partially used bottles, eCRF collect only millimetres left, the information from table 7 will be used to convert approximately the millimetres to millilitres. Each bottle will be assumed to contain 473mL, i.e. 139 millimetres. In case no kit/bottle is returned or all kits/bottles are declared as lost, the compliance will be considered as missing.

For patients with all dispensed tablets/sachets or bottles unused, reported as lost and no tablets/sachets or bottles returned dates, all exposure variables listed above excluding exposure durations and prescribed daily dose variables (maximum, average); and compliance will be set to missing.

For subjects who did not enter into Stage 2: all the records from the "Dispensation/Compliance" CRF Form will be assigned into Stage 1.

For subjects who entered into Stage 2: all the records from the "Dispensation/Compliance" CRF Form with a dispensed date < End of Stage 1 date -3 days will be assigned into Stage 1; the other records will be assigned into Stage 2.

Table 7 Approximate transformation from millimetres to millilitres to be used for Phoslyra compliance derivation

Phoslyra Bottle		
Millimetres (mm)	Millilitres (mL)	
139	473	
130	448	
120	411	
110	375	
100	339	
90	303	
80	268	
70	234	
60	200	
50	166	
40	130	
30	94	
20	59	
10	24	
1	1	

Linear interpolation will be used for millimetres not listed in table 7. The following formula will be applied:

 $mL = mL_0 + (mm - mm_0) * [ (mL_1 - mL_0)/(mm_1 - mm_0)]$ 

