#### Where

- mm is the observed value in millimetres for which approximate transformation in millilitres needs to be derived
- mL is the approximate transformation of mm in millilitres
- mm0 is the lower value in millimetres from table 7 compared to mm
- mm1 is the upper value in millimetres from table 7 compared to mm
- mL0 is the known value in millilitres (from table 7) for mm0
- mL1 is the known value in millilitres (from table 7) for mm1

Compliance (%) will be derived based on the sachets/tablets/bottles returned, reported as lost and dispensed and total prescribed dose during the stage considered.

All exposure data will be listed including the overall maximum dose prescribed (unit/day), overall maximum dose prescribed (unit/kg/day) and overall maximum dose received (unit/kg/day). In case subjects received both PA21 and Phoslyra during the study, one listing will be generated to display the list of subjects in that situation.

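### The single per-protocol set applies Stage 2 compliance to the supportive Stage 1 outputs, so subjects can be dropped for conduct after the endpoint

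*SAP*

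**What the plan says.** SAP Section 3.1 defines one PPS at subject level: FAS subjects with no major violation. Of its use it says: "This population will be analysed for the demographics and baseline characteristics, medical history as well as for the primary and secondary efficacy endpoints". The FAS is the primary efficacy population.

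Section 3.2 lists the major deviations that remove a subject from the PPS. The first is "Subject with insufficient compliance, i.e. missing, <70% or >120% during stage 1 or stage 2, (programmatically derived".

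Section 2.1 gives the timing: "Stage 1 is a dose titration period of PA21 and Phoslyra for up to 10 weeks". Subjects may move on from Week 4 once they reach target, and Stage 2 then lasts 24 weeks. Section 4.2.1 sets the boundary: "Stage 2 data will be defined as all data collected from the day after the last visit in the titration phase". The primary endpoint (Sections 2.5.1.1 and 4.7.1) is the change to the end of Stage 1 in the PA21 group.

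Section 4.6 already computes compliance by stage: "Compliance (%) will be derived based on the sachets/tablets/bottles returned, reported as lost and dispensed and total prescribed dose during the stage considered".

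Sections 7.1 and 7.3 list PPS versions of the Stage 1 change for PA21 and for Phoslyra (Table 14.2.2.2), and Stage 1 PPS Figures 14.2.1.2 and 14.2.2.2.

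**The concern.** A per-protocol result for an endpoint should describe subjects who adhered up to that endpoint. Here membership of the set behind the Stage 1 result also depends on what happens in the following 24 weeks. If the FAS and PPS results at the end of Stage 1 differ, or agree, the comparison cannot be read cleanly as showing the effect of adherence during Stage 1.

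A subject need not have misused the drug to be affected. Section 4.6 sets compliance to missing when no Phoslyra bottle is returned or all are declared lost, and in a defined set of lost or unreturned cases for either drug. If those rules are carried to each stage, unreturned Stage 2 supplies alone would remove a subject from the Stage 1 PPS outputs.

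What is at stake is the meaning of a supportive analysis, not the primary test.

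**Working it through.** **1. Trace one subject.** Take a subject with Stage 1 compliance between 70% and 120%, a valid End of Stage 1 value, no other deviation, and Stage 2 compliance below 70%.
- Section 3.2: the Stage 2 value is a major deviation.
- Section 3.1: a subject with a major deviation is not in the PPS, and there is only one PPS.
- Sections 7.1 and 7.3: the Stage 1 PPS tables and figures therefore omit this subject, although everything they report was observed before Stage 2 began.

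**2. Look for a limiting clause.** Sections 3.1, 3.2, 4.2.1, 4.6, 4.7 and 5 contain none. The output titles say only PPS Population.

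**3. Sort the Section 3.2 criteria by when they can occur.**

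| Criterion | Can arise after the End of Stage 1 assessment? |
|---|---|
| Eligibility, consent, baseline phosphorus | No |
| End of Stage 1 visit outside its window | No |
| Compliance | Yes, Stage 2 is named |
| Incorrect study treatment; receipt of both drugs | Yes, no stage is stated |
| Others added at the blinded review | Open |

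Compliance is the only listed criterion that names Stage 2, but the two treatment criteria have the same gap.

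**4. Subjects who did not enter Stage 2.** Section 3.2 counts missing compliance as a failure and does not say whether a non-entrant's Stage 2 compliance is missing. Section 3.1 has "Stage 2 Safety Population: all subjects who have taken at least one dose of study medication during stage 2". Section 4.6 summarises Stage 2 exposure, compliance included, "on the Stage 2 Safety Population for stage 2 exposure data", and adds "For subjects who did not enter into Stage 2: all the records from the 'Dispensation/Compliance' CRF Form will be assigned into Stage 1". Together these point to not applicable.

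**5. Count the outputs.** PPS outputs listed: 9 demographic, baseline and history tables + 2 Stage 1 endpoint tables + 1 Stage 2 endpoint table + 6 over-time tables + 4 figures = 22. Directly affected are the 2 Stage 1 tables and 2 Stage 1 figures, 4 in all. The 6 over-time tables also show Stage 1 visits.

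**6. Timing.** Share of nominal treatment time after the endpoint: 24/(10 + 24) = 24/34 = 71%, or 24/(4 + 24) = 24/28 = 86% for a subject who moves on at Week 4. These are shares of weeks only.

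**7. Size.** The one related figure in the SAP is the power in Section 4.1. With n = 100 × (1 − 0.30) = 70, mean change 1.2 mg/dL and SD 2.0, the noncentrality is (1.2/2.0) × √70 = 5.02. A two-sided 0.05 one-sample t-test then has power 99.86%, so the claim of more than 90% holds. It says nothing about the PPS.

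If a fraction f of Stage 1 compliers is dropped, and their mean Stage 1 change differs by D from that of the subjects kept, the PPS mean moves by f × D. The SAP gives neither. Purely as assumptions, f = 10% to 30% and D = 0.5 to 1.0 mg/dL give 0.10 × 0.5 = 0.05 to 0.30 × 1.0 = 0.30 mg/dL. This shows how the mechanism scales. It is not an estimate.

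**The case against.** The strongest defence is that one study-wide PPS of subjects adherent throughout is a deliberate choice, applied consistently in Sections 3.1, 3.2 and 7, which keeps the same subjects in every PPS output. This stands to the extent that the SAP does not contradict itself and that a common set has some value. It does not answer why an endpoint reached at Week 4 to 10 should depend on a 24-week extension, in a plan that already has a Stage 2 Safety Population and compliance by stage.

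A second defence is that the blinded data review settles deviations before lock. Section 3.2 lists the compliance criterion outright as major and programmatically derived, and its open category adds deviations. It does not provide for waiving a listed one.

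A third is that the PPS is supportive and no consequence has been shown. This stands, and it limits the severity.

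Three stronger readings are tempting and not supported:
- A reader might infer that the primary result is biased. The primary analysis uses the FAS, which has no compliance criterion.
- A reader might take 71% or 86% as the share of subjects or information lost. Compliance is one value per stage, so the length of Stage 2 does not show how often that value fails.
- A reader might infer that everyone who withdrew in Stage 1 is dropped for missing Stage 2 compliance. Section 4.6 points the other way, and only a clarifying phrase is lacking.

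**Conclusion.** The point holds as a fault in the definition of the supportive analysis set. As written, the Stage 1 PPS outputs exclude subjects for Stage 2 compliance and, by the same gap, for treatment mix-ups that occur only in Stage 2.

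The conclusion rests on reading Sections 3.1 and 3.2 as they stand, with one PPS and no unstated stage limit. Neither the number of subjects affected nor the direction of any shift can be derived from the SAP. Severity is low to moderate, and the change is a cheap improvement.

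**What to change.** Define two sets in Section 3.1 and tie the Section 3.2 criteria to them, with thresholds unchanged. Suggested content:

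- *Stage 1 PPS, for Stage 1 endpoints and visits:* only Stage 1 compliance is considered. Incorrect study treatment and receipt of both drugs count only if they occurred up to the End of Stage 1 assessment.
- *Stage 2 PPS, for Stage 2 endpoints and visits:* Stage 1 and Stage 2 criteria both apply. For subjects who did not enter Stage 2, Stage 2 compliance is not applicable and is not counted as missing.
- Deviations added at the blinded review are dated and assigned by the same rule.

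Then state the set for each of the 22 PPS outputs:
- The 4 Stage 1 endpoint outputs use the Stage 1 PPS.
- The 9 demographic, baseline and history tables use the Stage 1 PPS.
- The 6 over-time tables (14.2.4.2, 14.2.4.4, 14.2.5.3, 14.2.5.4, 14.2.6.3, 14.2.6.4) name the set by stage.
- The 3 Stage 2 outputs (Table 14.2.3.2, Figures 14.2.1.4 and 14.2.2.4) use the Stage 2 PPS. Figure 14.2.2.4 should say which set applies to any Stage 1 time points.

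Table 14.1.2, Table 14.1.3.3 and Listing 16.2.3 should show both sets with their Ns.

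The cost is SAP wording before database lock, one compliance flag per stage (Section 4.6 already supplies the values), and a date condition on the two treatment criteria. The downside is that Stage 1 and Stage 2 PPS outputs may contain different subjects, and the over-time tables change membership at the stage boundary, so each needs its own N. The Stage 2 PPS is nested within the Stage 1 PPS but would have no baseline table of its own unless one is added.
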